# EMAILS: E-learning to Maximize Academic Inclusion of LGBTQ+ Students

The active control, EMAILS, is an email-based intervention in which existing online resources for supporting, affirming, and protecting LGBTQ+ are emailed to participants. These resources are also provided to intervention participants. The topics covered by EMAILS are similar to those of PLANTS, though there are some unique aspects to PLANTS. This intervention is informed by the Information-Motivation-Behavior theory as well. EMAILS includes the following publicly available materials:

- Adagio Health LGBTQ+ Professionalism Training (https://youtu.be/VX9tDt3gOto)
- Imi (Audience is LGBTQ+ teens, https://imi.guide/)
- The Safe Zone Project (https://thesafezoneproject.com/)

These intervention activities include self-paced modules, YouTube videos, and PowerPoints. There is no direct human interaction in this intervention other than email. EMAILS participants are individually emailed using a duration and pace similar to PLANTS (e.g., lasts 3 months). The intervention takes place entirely online. We will not be doing any tailoring of these materials to specific audiences, other than compiling various resources. We will monitor active control compliance and fidelity via email clicks by sending emails with training links from REDCap to participants, and then participants click on the training links in Qualtrics for tracking purposes. We will also use follow-up survey questionnaires to assess use of EMAILS.

# 6.1.2 Administration and Dosing

PLANTS online modules will be administered online via Canvas. Sections will be opened once per month, and there are a total of 3 sections over 3 months. The synchronous Live Events will be administered via Zoom. There are a total of 3 events. A "Full Dose" of the PLANTS intervention includes completion of all the online modules and 3 Live Zoom Events. The Live Zoom Events are required to be administered by trained interventionists (the PI or Research Assistants). In the Live Zoom Events, participants will interact with each other and a shared interventionist in a virtual environment. Active control materials cannot be tracked as easily

because these online trainings are administered via other agency's websites (not the study team's website). There are no interventionists in the active control arm.

# 6.2 Fidelity

### 6.2.1 Interventionist Training and Tracking

The PLANTS Live Zoom Events require effort be made to check that the intervention is appropriately conducted by the interventionists. For each Live Zoom Event, the research assistant(s) will keep detailed notes of the sessions. We will then check these notes against the change methods and learning objectives for each module to ensure fidelity of the intervention. We will also monitor implementation of the PLANTS asynchronous online modules by checking that the release dates are met in the online platform. We use Canvas Learning Management Software to deliver PLANTS. We will monitor intervention compliance and fidelity via module questionnaires, Canvas informatics, event attendance, and follow-up survey questionnaires.

EMAILS has no direct human interaction in this intervention other than email. We will track delivery of EMAILS by checking sent emails against an implementation plan. We will monitor active control compliance and fidelity via email clicks by sending emails with training links from Qualtrics to participants, and then participants click on the training links in Qualtrics for tracking purposes. We will also use follow-up survey questionnaires to assess use of EMAILS.

#### 6.3 Measures to Minimize Bias: Randomization and Blinding

We will randomize schools in an equal 1:1 ratio, stratified by large versus small schools, into intervention or active control conditions. We will use permuted block allocation (with block size=2) to randomize schools to the intervention or active control conditions. We use block size of 2 because there are only 4 schools in this pilot trial. The permuted blocks will be created using the "ralloc" package for Stata. We will use REDCap's Randomization Module. We will randomize schools after they enroll in the study, but before school staff complete baseline surveys. [name] will create the randomization files in Stata, and the study coordinator will allocate schools to conditions in REDCap. We will conceal allocation from schools.

This is an unblinded study. This is an educational intervention that cannot be blinded because study participants will be able to tell which condition they are in based on the content they receive. Unblinding could introduce bias, including social desirability bias, attrition bias, bias in intervention participation, and bias in reporting adverse events. Outcomes are assessed via self-reported online surveys, so there is no concern about bias about the blinding for outcome assessors. We do not anticipate planned or unplanned breaking of randomization allocation to participants or schools.

#### 6.4 Study Intervention Adherence

We will make the following efforts to confirm that the subject of the PLANTS intervention is adherent:

- Participants will be required to click "completed" in Canvas modules when they are completed.
- We will ask participants to register for the Live Zoom Events.
- We will track attendance at Live Zoom Events.
- We will contact participants if they have yet to complete the modules or Live Zoom Events.

Canvas module completion and Live Zoom Event attendance will be used to calculate study intervention adherence.

#### PLANTS Pilot Trial Protocol STUDY21080178 For the active control arm, we will ask participants to self-report completion of the online trainings in questionnaires sent after each email and in the follow-up survey if they completed the trainings.

#### 6.5 Concomitant Therapy

N/A

#### 6.5.1 Rescue Therapy

N/A

# 7 STUDY INTERVENTION DISCONTINUATION & PARTICIPANT DISCONTINUATION/WITHDRAWAL

#### 7.1 Discontinuation of Study Intervention

N/A

#### 7.2 Participant Discontinuation/Withdrawal from the Study

Participants are free to withdraw from participation in the study at any time upon request. An investigator may discontinue a participant from the study for the following reasons:

- Lost-to-follow up; unable to contact subject
- The participant meets an exclusion criterion (either newly developed or not previously recognized) that precludes further study participation

The reason for participant discontinuation or withdrawal from the study will be recorded on the Protocol Deviation Form. Subjects who sign the informed consent form and subsequently withdraw, or are discontinued from the study, will not be replaced.

#### 7.3 Lost to Follow-Up

A participant will be considered lost to follow-up if they fail to complete the follow-up survey and study staff are unable to contact the participant after at least 3 attempts.

The following actions must be taken if a participant fails to complete a study visit:

- Staff will attempt to contact the participant, encourage completion of the study activity, counsel the participant on the importance of maintaining study participation, and ascertain if the participant wishes to continue in the study.
- Before a participant is deemed lost to follow-up, staff will make every effort to regain contact with the participant (where possible, 3 telephone calls, 3 texts, and 3 emails, if necessary). These contact attempts will be documented in the participant's study file.
- Should the participant continue to be unreachable, the participant will be considered lost to follow-up.

# 8 STUDY ASSESSMENTS AND PROCEDURES

#### 8.1 Endpoint and Other Non-Safety Assessments

School Screener

Version 1.0

2024.04.05

- 1. Inclusion/exclusion will be assessed over Qualtrics, the phone, Zoom, or in-person by study staff to school administrators. These are the exact questions:
  - a. Does your school plan to participate in the 2023 MetroWest Adolescent Health Survey?
  - b. Does your school plan to participate in the 2025 MetroWest Adolescent Health Survey?
  - c. Does your school grant us permission to access your MWAHS data?
  - d. Will your school provide emails addresses for all school staff so we can recruit them to the trial?
  - e. Will your school provide our team with a letter of support denoting their participation in our study?
- 2. Public school data: We will gather all publicly available data from the Massachusetts Department of Elementary and Secondary Education website, including school size.
- 3. Randomization: Upon enrollment of a school, we will randomize them to either PLANTS or EMAILS based on our stratified blocked randomization.

# Staff Screener (Time 0)

- 1. Inclusion/exclusion will be self-administered via REDCap by high school staff. These are the exact questions:
  - a. Which schools do you currently work at? [drop down list of MetroWest Schools + "Somewhere else" + write-in]
  - b. How often do you interact with students at your job? [0: Daily; 1: Weekly; 2: Monthly; 3: Yearly; 4: Never]
  - c. How old are you? [integer validation]
- 2. Informed consent: We will provide informed consent materials online via REDCap.

# Staff Baseline Survey (Time 1)

These surveys are self-administered online via REDCap by high school staff. The following measures are included in the baseline surveys:

- 1. **Demographics:** We assess schools staff's role(s) in school, years working as a staff member, age, race/ethnicity, gender identity (including transgender status), sex assigned at birth, sexual identity, past contact with sexual and gender minorities, past encounters working with SGMY, previous professional development related to working with SGMY, highest education level achieved, religious affiliation, and religiosity. We also measure attitudes towards LGBTQ people using the Modified Attitudes Toward Lesbians and Gay Men (Herek & McLemore, 2011; Strong, 2013) Scale. 78-80 This scale has four subscale domains about attitudes towards: gay men ( $\alpha$  range = 0.75-0.76); lesbian women ( $\alpha$  range 0.76-0.79); bisexual people; ( $\alpha$  range = 0.79-0.81; lesbian women ( $\alpha$  range  $(0.76-0.79)^{81}$ ; bisexual people; ( $\alpha$  range =  $(0.79-0.81)^{81}$ ; transgender people ( $\alpha$  range =  $(0.79)^{81}$ ; and nonbinary people (newly created). Each subscale has three items (e.g., "Having sex with both males and females is just plain wrong"). Response options included a five-point Likert scale ranging from "strongly agree" to "strongly disagree."
- 2. Active-empathic listening skills: We use the valid and reliable Active-Empathic Listening Scale containing 11 items (Bodie, 2011; Gearhart & Bodie, 2011). This scale has three domains: sensing (4 items; e.g., "I listen for more than just the spoken words"); processing (3 items; e.g., "I summarize points of agreement and disagreement when appropriate"); and responding (4 items; e.g., "I assure others that I am listening by using verbal acknowledgements"). Response options included a 7-point Likert scale ranging from "Never or almost never true" to "always or almost always true." We will

# PLANTS Pilot Trial

calculate the mean score for the total scale. Prior research shows Cronbach's alphas range from 0.88-0.90.

- **3. Self-efficacy for working with SGMY**: We assess participants' perceived abilities for working with LGBTQ high school students using 9 items adapted from the Gay Affirmative Practice Scale. Originally for social work practitioners, we adapted this scale by using school-oriented words instead of therapy-oriented words (e.g., "students" instead of "clients"). Example items included "I am able to help LGBTQ students develop positive identities as LGBTQ individuals" and "I am able to challenge misinformation about LGBTQ individuals in the classroom." Response options included a five-point Likert scale ranging from "strongly agree" to "strongly disagree." We will calculate the mean score for the scale. In a prior study, Cronbach's alpha = 0.90.
- **4. Bystander intervention behaviors for bullying:** Two multidimensional scales (Teacher Bystander Intervention Model in Traditional Bullying and Cyberbullying) measuring 5 subscales of bystander behaviors each: noticing the event (3 items), interpreting event as an emergency (3 items); accepting responsibility to help (3 items); knowing how to help (3 items); and implementing intervention decision (4 items). The psychometric properties of these subscales are good (Cronbach's alphas range=0.57-0.88). We will calculate average subscale scores. We will add items to these scales to specify SGMY-related bullying events using language from GLSEN's National School Climate Survey.
- 5. Self-efficacy of PLANTS' change objectives: Given the limited research contained validated scales of behavior change pertaining to LGBTQ inclusive practices in schools, our team has developed items pertaining directly to the self-efficacy change objectives in PLANTS. Each question will be asked on a scale of 1-5 (1: not at all certain; 2: slightly certain; 3: moderately certain; 4: very certain; 5: extremely certain).
  - a. **Provide interpersonal support and affirmation.** How certain are you that you are able to successfully: ask students about their chosen names? Use students' chosen names? Ask students about their pronouns? Use students' pronouns? use "reinforcing language" with students? "affirmations" with students? share about your personal connections to the LGBTQ+ community with your LGBTQ+ students?
  - b. Support LGBTQ+ students in meeting their basic needs. How certain are you that you are able to successfully: offer safe locations where gender diverse youth can use the bathroom (e.g., gender neural bathrooms, staff bathrooms)? offer non-stigmatizing locations where gender diverse youth can use the bathroom (e.g., gender neural bathrooms, staff bathrooms)? Offer nearby locations where gender diverse youth can use the bathroom (e.g., gender neural bathrooms, staff bathrooms)? Offer nearby locations where gender diverse youth can use the bathroom (e.g., gender neural bathrooms, staff bathrooms)? refer LGBTQ+ students to LGBTQ affirming outside-school resources?
  - c. **Provide educational resources that are inclusive of LGBTQ+ students.** How certain are you that you can successfully: find LGBTQ+ resources? put LGBTQ+ resources where students can easily access them? defend LGBTQ+ inclusive curriculum? integrate LGBTQ+ people, history, or issues into your coursework? Implement LGBTQ+ inclusivity in your curriculum? assess curriculum for LGBTQ+ inclusivity? inform students about LGBTQ+ resources?
  - d. **Provide safe spaces for LGBTQ+ students.** How certain are you that you can successfully: wear iconography of LGBTQ+ pride and acceptance? display iconography of LGBTQ+ pride and acceptance for their rooms/offices? display iconography of LGBTQ+ pride and acceptance in common areas? observe LGBTQ+ related holidays and events? Establish a gender-sexuality alliance? Oversee a gender-sexuality alliance? be a Point Person? Provide LGBTQ+ students with a safe space?

- e. **Promote acceptance of LGBTQ+ students among non-LGBTQ+ students.** How certain are you that you can successfully: politely correct people who use students' incorrect names? politely correct people who use students' incorrect pronouns? teach students about LGBTQ+ terminology in a positive manner? provide positive verbal reinforcement when non-LGBTQ+ students do something LGBTQ-inclusive?
- f. Prevent and reduce bullying, cyberbullying, and harassment of LGBTQ+ students. How certain are you that you can successfully: define anti-LGBTQ+ bullying and harassment? implement classroom guidelines and meetings? intervene in anti-LGBTQ+ bullying and harassment? convene an anti-LGBTQ+ bullying task force when necessary? follow-up with victims and bystanders of anti-LGBTQ+ bullying? use non-confrontational ways to engage with perpetrators of anti-LGBTQ+ bullying? enforce clear consequences for people who bully others? explain to students why anti-LGBTQ+ bullying is harmful and wrong? advocate for evidence-based bullying prevention programming?
- g. Evaluate and advocate for LGBTQ+ inclusivity and protections in school policies. How certain are you that you can successfully: obtain LGBTQ+ students' feedback about the inclusivity and protections for LGBTQ+ students in existing school policies? Amend/dismantle school policies and practices that negatively affect LGBTQ+ students? evaluate how inclusive and protective their school policies are for LGBTQ+ students and staff? share statistics to advocate for LGBTQ+ inclusivity and protections in school policies? share personal stories to advocate for LGBTQ+ inclusivity and protections in school policies? use required methods (e.g., school board propositions) to create/amend school policy? examine how well your school's LGBTQ+ related policies align with local, state, and federal school laws and policies?
- h. **Maintain the confidentiality of LGBTQ+ students.** How certain are you that you can successfully: keep students' sexual orientations confidential? keep students' gender identities confidential? make students aware of mandatory reporting guidelines? assess students' safety concerns surrounding disclosure of their LGBTQ+ identity? establish or amend school policies that protect the confidentiality of students' sexual orientations and gender identities?
- 6. Social desirability bias: We will assess school staff's social desirability biases using the short form of the Marlowe-Crowne Social Desirability Scale. The short form of the scale uses 13 self-reported measures of individual characteristics, such as personality and attitudes, to understand the social desirability bias of individuals. The psychometric properties of this scale have shown it to be reliable compared to the Social Desirability Scale developed by Edwards; its use has been studied for both adolescents and adults. We will calculate the social desirability biases of each school staff member based on their responses to the measures during the baseline survey.
- **7. Existing school programs:** We will ask each staff member about their school's presence and types of bullying prevention programs, substance use prevention/treatment program, mental health prevention/treatment programs, intervention programs and policies for SGMY.

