#### Study Flow of Two-Arm Cluster-Randomized Controlled PLANTS Pilot Trial, Nested within the MetroWest Adolescent Health Survey Infrastructure

#### PLANTS Pilot Trial Protocol STUDY21080178 **1.3 Schedule of Activities**

	School Screener	Staff Screener (Time 0)	Staff Baseline Survey (Time 1)	PLANTS Program	Control Program	Staff Follow-up Survey (Time 2)	Staff Follow-up Interview (Time 3)
SCHOOL DATA							
Inclusion/exclusion	Х						
Public school data	Х						
Randomization	Х						
STAFF DATA							
Inclusion/exclusion		X X					
Informed consent		Х					
Demographics			Х			Х	
Social desirability			Х			x	
bias			^			^	
Existing school			х			x	
programs			^			^	
Primary Outcomes							
Intervention Acceptability, Usability, Appropriateness, and Feasibility				х		x	x
Secondary							
Outcomes							
Implementation Outcomes	Х	Х	Х	Х	Х	x	Х
Adverse Events Reporting			Х	Х	Х	х	х
Active Empathetic Listening			Х	Х		Х	Х
Self-efficacy for			Х	Х		х	х
Working with SGMY Self-efficacy of PLANTS' Change			х	х		x	x
Objectives Bystander Intervention Behaviors for Bullying			х	х		x	x

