# **3 OBJECTIVES AND ENDPOINTS**

OBJECTIVES	ENDPOINTS	JUSTIFICATION FOR ENDPOINTS
Primary		
To evaluate the acceptability, usability, appropriateness, and feasibility of PLANTS	In the follow-up survey, school staff will complete the following survey measures: - Acceptability of Intervention Measure - System Usability Scale - Intervention Appropriateness Measure - Feasibility of Intervention Measure	We use validated scales that assess high school staff's perceptions of the intervention's tolerability, user friendliness, fit, relevance, and successful execution.
Secondary		
To test the efficacy of PLANTS intervention for improving SGMY behaviors among high school staff	-Active empathic listening -Self-efficacy for supporting, affirming, and protecting SGMY -Self-efficacy of PLANTS change objectives -Positive bystander intervention behaviors	PLANTS is specifically designed to target these behavioral outcomes.

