- a. **Provide interpersonal support and affirmation.** How certain are you that you are able to successfully: ask students about their chosen names? Use students' chosen names? Ask students about their pronouns? Use students' pronouns? use "positive teacher language"? share about your personal connections to the LGBTQ+ community with your LGBTQ+ students?
- b. **Support LGBTQ+ students in meeting their basic needs.** How certain are you that you are able to successfully: offer safe locations where gender diverse youth can use the bathroom (e.g., gender neural bathrooms, staff bathrooms)? offer non-stigmatizing locations where gender diverse youth can use the bathroom (e.g., gender neural bathrooms, staff bathrooms)? Offer nearby locations where gender diverse youth can use the bathroom (e.g., gender neural bathrooms, staff bathrooms)? Offer nearby locations where gender diverse youth can use the bathroom (e.g., gender neural bathrooms, staff bathrooms)? refer LGBTQ+ students to LGBTQ affirming outside-school resources?
- c. **Provide educational resources that are inclusive of LGBTQ+ students.** How certain are you that you can successfully: find LGBTQ+ resources? put LGBTQ+ resources where students can easily access them? defend LGBTQ+ inclusive curriculum? integrate LGBTQ+ people, history, or issues into your coursework? Implement LGBTQ+ inclusivity in your curriculum? assess curriculum for LGBTQ+ inclusivity? inform students about LGBTQ+ resources?
- d. **Provide safe spaces for LGBTQ+ students.** How certain are you that you can successfully: wear iconography of LGBTQ+ pride and acceptance? display iconography of LGBTQ+ pride and acceptance for their rooms/offices? display iconography of LGBTQ+ pride and acceptance in common areas? observe LGBTQ+ related holidays and events? Establish a gender-sexuality alliance? Oversee a gender-sexuality alliance? be a Point Person? Provide LGBTQ+ students with a safe space?
- e. **Promote acceptance of LGBTQ+ students among non-LGBTQ+ students.** How certain are you that you can successfully: politely correct people who use students' incorrect names? politely correct people who use students' incorrect pronouns? teach students about LGBTQ+ terminology in a positive manner? provide positive verbal reinforcement when non-LGBTQ+ students do something LGBTQ-inclusive?

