# PLANTS Pilot Trial Version 1.0 Protocol STUDY21080178 2024.04.05 Hypothesis: High school staff participants in the PLANTS arm will report pre-post improvements in active- empathic listening, self-efficacy for supporting, affirming, and protecting sexual and gender minority youths, and positive bystander intervention behaviors for bullying.

To examine the pre-post changes in high school staff outcomes, investigators will first use descriptive statistics, such as means and percentages at each timepoint within arms. To test for within-arm statistical significance, investigators will use linear mixed models for continuous outcomes and generalized linear mixed models for binary outcomes, which account for within-school and within-person clustering using random effects. Investigators will estimate the intraclass correlations for within-school and within-person effects. These models will adjust for school size (*a priori* design variable).

Hypothesis: Participants in PLANTS will report greater active-empathic listening, greater self-efficacy for supporting, affirming, and protecting SGMY, and greater positive bystander intervention behaviors for bullying in follow-up surveys than participants in the active control arm.

We will use linear mixed models for continuous outcomes and generalized linear mixed models for binary outcomes—which account for within-school and within-person clustering effects (using random effects). We will estimate the intraclass correlations for within-school and within-person effects. Regression models will include a fixed term for school size (a priori design variable), intervention group (intervention or control), time (baseline or follow-up), and the interaction of intervention group × time (our variable of interest). The test of intervention effects on secondary outcomes will be primarily based on intent-to-treat estimates. We will estimate perprotocol effects in secondary models. If there are differences in potential confounders by intervention group, we will adjust for them in secondary multivariable analyses.

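### One domain of the change-objectives self-efficacy measure asks different questions at baseline and follow-up, and no rule restricts change to the questions asked at both times

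*Combined protocol and SAP*

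**What the plan says.** Section 3 lists "Self-efficacy of PLANTS change objectives" among the secondary efficacy endpoints, and the Schedule of Activities (1.3, row "Self-efficacy of PLANTS' Change") places it at both the baseline and the follow-up survey. The team wrote the items. Section 8.1 prints them by domain (a to h) for each survey, each answered on a 1 to 5 certainty scale.

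In domain a, baseline item 5a includes "use 'reinforcing language' with students? 'affirmations' with students". Follow-up item 7a has instead a single prompt on whether staff can "use 'positive teacher language".

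In the baseline section the other three efficacy measures each have a scoring rule. Active-empathic listening gets a mean total score. For the adapted self-efficacy scale the text is "We will calculate the mean score for the scale", and for the bystander scales "We will calculate average subscale scores". The change-objectives measure has only its response scale, at both times.

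Section 9.4.1 plans exploratory factor analysis and internal consistency for newly created items, using baseline surveys. Section 9.4.3 covers "pre-post changes in high school staff outcomes, investigators will first use descriptive statistics, such as means and percentages at each timepoint within arms", followed by mixed models within arm and then a between-arm model with a group-by-time term. Neither section says which prompts make up the outcome.

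**The concern.** A pre-post comparison needs the same questions on both occasions. If domain a is scored on whatever was asked each time, staff whose confidence has not moved can still show a change, because one or two prompts have left the score and another has entered. The direction is not known in advance: replacing prompts on which staff feel less sure with an easier one looks like improvement, and the reverse hides it.

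The exposure is in the PLANTS-only change. That is the figure a reader would take as a signal that the course works on interpersonal support and affirmation, the first behavioral outcome the protocol names for PLANTS. The planned factor analysis offers no protection: run on baseline data, it would include the dropped wording and never examine the follow-up prompt.

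**Working it through.** **Step 1: match the prompts (section 8.1, items 5a and 7a).**

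| Domain a prompt | Baseline | Follow-up |
|---|---|---|
| Asking chosen names | yes | yes |
| Using chosen names | yes | yes |
| Asking pronouns | yes | yes |
| Using pronouns | yes | yes |
| Reinforcing language | yes | no |
| Affirmations (no verb printed) | yes | no |
| Positive teacher language | no | yes |
| Sharing personal connections | yes | yes |

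Baseline has 7 prompts as printed, or 6 if the verbless one belongs to the prompt before it. Follow-up has 6. Five are common on either reading. Domains b to h match as printed.

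**Step 2: the artefact on a domain mean.** The plan states no figure to reproduce and no score, so a simple mean is assumed. Let the common prompts average m at both times (no true change), the replaced baseline prompts average m + d1, and the new follow-up prompt m + d2.

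- Baseline, 7-prompt reading: (5m + 2(m + d1))/7 = m + 2·d1/7
- Baseline, 6-prompt reading: (5m + m + d1)/6 = m + d1/6
- Follow-up: (5m + m + d2)/6 = m + d2/6
- Apparent change: d2/6 − 2·d1/7 (7-prompt) or (d2 − d1)/6 (6-prompt)

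| Assumption | 7-prompt | 6-prompt |
|---|---|---|
| Largest, both deviations within 1 point | 1/6 + 2/7 = 0.452 | 2/6 = 0.333 |
| Largest, both within 0.5 | 0.226 | 0.167 |
| Largest, both within 0.25 | 0.113 | 0.083 |
| Old prompts 1 lower, new one equal to common | +0.286 | +0.167 |
| Old and new both 1 lower | +0.119 | 0 |

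The first three rows need old and new prompts to deviate in opposite directions. As an example on the 7-prompt reading, common prompts at 4, old at 3 and new at 4 give (20 + 6)/7 = 3.71 and (20 + 4)/6 = 4.00, an apparent gain of 0.29 with no change on any common prompt. A sum score, which the plan does not exclude, would fall from 21 to 18 with every answer at 3, simply because there is one prompt fewer.

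**Step 3: the artefact on a mean of all prompts.** Domains b to h have 5 + 7 + 8 + 4 + 9 + 7 + 5 = 45 prompts as printed, giving 52 (7-prompt) or 51 (6-prompt) at baseline and 51 at follow-up. With deviations within 1 point, the maximum is 1/51 + 2/52 = 0.058 or 2/51 = 0.039. Domain b prints "Offer nearby locations where gender diverse youth can use the bathroom" twice at both times; counting it once gives 0.059 or 0.040.

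**Step 4: compare with sampling error.** Section 9.2 gives 344 × 0.5 × 0.5 × 0.75 = 64.5, stated as 65 PLANTS completers. The 95% half-width for a mean change is t(0.975, 64) × SD/√65. The documents give no SD of change, so a range is assumed:

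| Assumed SD of change | Half-width |
|---|---|
| 0.5 | 0.124 |
| 0.6 | 0.149 |
| 0.8 | 0.198 |
| 1.0 | 0.248 |

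This ignores clustering by school. The 0.452, 0.333 and 0.286 cases exceed the whole range and 0.167 falls inside it. The equal-deviation case (0.119) and the all-prompt cases do not exceed it.

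**Step 5: after the fix.** Scored on the five common prompts, unchanged answers give a change of exactly zero.

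**The case against.** The strongest reply is that the wording participants will see is not established. The protocol calls its screener questions exact but makes no such claim for the surveys, and the item lists read like unfinished drafting. That is fair: this may be a slip in the document and not in the forms. But the two lists are the only specification of the instrument available, and they disagree.

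Second, the hypotheses in 9.4.3 name self-efficacy for supporting, affirming and protecting these students, which section 3 lists separately from the change-objectives measure, so the pre-post test may not cover it. This stands as an uncertainty. The analysis text speaks of staff outcomes generally, and section 3 lists this measure among the efficacy endpoints.

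Third, both arms receive the same forms, so a common shift cancels in the group-by-time term, and equally in the three-way interactions of the subgroup models in 9.4.7. It would also be visible in the EMAILS arm's descriptive change. This is correct, provided the arms react alike to the new phrase. It leaves the within-arm change exposed.

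Fourth, domain a may never be scored as a unit, because the factor analysis could define other dimensions, and the larger artefacts need old and new prompts to deviate in opposite directions. Nothing in the documents supports such deviations. This limits the size, but factor analysis of baseline data is not a scoring rule and cannot place a prompt asked only at follow-up.

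The repeated domain b prompt is the same at both times and contributes nothing to the mismatch.

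**Conclusion.** The concern holds. As written, a listed secondary endpoint would be compared over time on questions that are not identical, with nothing to confine the comparison to those that are.

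The reach is limited: one of eight domains, in one of four secondary efficacy measures. The size depends on an undefined score and on deviations the documents do not give. On a domain a mean it runs from zero to 0.45 for deviations within 1 point, and the upper part of that range exceeds the assumed sampling error. On an all-prompt mean it is negligible. That the printed lists differ is certain; that the fielded forms differ is not. The point should be corrected, but it does not threaten the trial's main conclusions.

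**What to change.** Use the same domain a prompts at Time 1 and Time 2, and make items 5a and 7a in section 8.1 agree. If baseline has already been fielded, either restore the baseline wording in the follow-up form or add a sentence to 9.4.3: change in this measure is scored only on prompts asked at both times (five in domain a), with non-matching prompts reported descriptively. That sentence is the natural place to say how the measure is scored. It should be fixed before follow-up data are seen, so that the choice of score cannot depend on the results.

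The cost is an edit to one block of the REDCap follow-up form, or one sentence in the plan. At worst, one or two baseline prompts and one follow-up prompt drop out of the change analysis.
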